10.5 Quality Assurance Audits and Health Authority Inspections

The clinical investigator study site may be patient to quality assurance audits performed by Clinsearch or its agents on behalf of Clinsearch, and/or regulatory inspections by the appropriate health authorities. The Investigator and the institution will allow Clinsearch, its agents, and/or appropriate regulatory authorities direct access to study records including source records, CRFs and other study relevant documentation for review. Patient privacy and data confidentiality will be observed accordingly to the applicable regulatory requirements and/or local laws.

The Investigator must immediately notify Clinsearch if they have been contacted by a regulatory agency concerning an upcoming inspection. It is important that investigators and their relevant personnel are available during audits and/or inspections and that sufficient time is devoted to the process.

10.6 Publication of study protocol and results

Clinsearch confirms that a synopsis of the study results will be submitted to the authorities and the Ethics Committees in ICH E3 format within one year after the end of the clinical trial. Furthermore, protocol information and clinical results will also be submitted in EudraCT within one year after the end of the clinical trial. In addition, upon study completion and finalization of the study report the results of this study will be either submitted for publication and/or posted in other publicly accessible database of clinical study results.

11 Protocol adherence

Investigators ascertain they will apply due diligence to avoid protocol deviations. Under no circumstances should the Investigator contact Clinsearch or its agents, if any, monitoring the study to request approval of a protocol deviation, as no authorized deviations are permitted. If the Investigator feels a protocol deviation would improve the conduct of the study this must be considered a protocol amendment, and unless such an amendment is agreed upon by Clinsearch and approved by the IRB/IEC/REB it cannot be implemented. All significant protocol deviations will be recorded and reported in the CSR, as defined in the note for Guidance ICH E3.

11.1 Protocol Amendments

Any change or addition to the protocol can only be made in a written protocol amendment that must be approved by Clinsearch, Health Authorities where required, and the IRB/IEC/REB. Only amendments that are required for patient safety may be implemented prior to IRB/IEC/REB approval. Notwithstanding the need for approval of formal protocol amendments, the Investigator is expected to take any immediate action required for the safety of any patient included in this study, even if this action represents a deviation from the protocol. In such cases, Clinsearch should be notified of this action and the IRB/IEC/REB at the study site should be informed within 10 working days.

WHO	World He	World Health Organization			
WOCBP	Women of	Women of child-bearing potential			

CRMB	Trial Substance:	Esflurbiprofen Hydrogel Patch	Study No.: TK-254R-0201 EudraCT No.: 2020-005165-14
	Short Title:	Local symptomatic and short-term treatment of pain in acute strains, sprains or bruises of the extremities following blunt trauma	Sponsor: TEIKOKU SEIYAKU CO LTD.

1 INTRODUCTION

General information on methods and procedures for the statistical evaluation are described in the Clinical Study Protocol (CSP), Final Version 3.0 dated 08 March 2021. The Statistical Analysis Plan (SAP) presented here outlines the evaluations to be performed in the final statistical analysis, including details with respect to endpoint derivation, applied statistical methods, and presentation of the results.

This SAP refers to the latest version of the Study Protocol. There were no amendments to the CSP in this clinical trial. The SAP will be finalized after the Data Blind Review Meeting (DBRM) and contains a comprehensive and detailed elaboration of the statistical methodology section of the protocol.

2 DESIGN OF THE CLINICAL TRIAL

The study is a Phase II (proof-of-concept), randomized, double-blind, multi-center, placebocontrolled, parallel group clinical trial of the efficacy and safety of Esflurbiprofen Hydrogel Patch applied once a day versus placebo patch applied once a day in the local symptomatic and short-term treatment of pain in acute strains, sprains or bruises of the extremities following blunt trauma, conducted in Germany.

It is planned to include a total of 200 patients (100 patients per active group and 100 per placebo group) in 3 sites.

The duration of each patient's participation in the study will be 7 (+1) consecutive days (from randomization (V1) to Final Visit (V7)).

3 TIME SCHEDULE

The study consists of 7 visits: randomization visit (Visit 1, 0 h, Day 1), and post-baseline visits Visit 2 (12 h (\pm 1 h) after first treatment, Day 1 or 2), Visit 3 (24 h (\pm 2 h) after first treatment, Day 2), Visit 4 (48 h (\pm 4 h) after first treatment, Day 3), Visit 5 (72 h (\pm 4 h) after first treatment, Day 4), Visit 6 (96 h (\pm 4 h) after first treatment, Day 5) and Visit 7 (168 h (\pm 24 h) after first treatment, Day 8 (\pm 2 days)). A detailed schedule of Assessments is presented in the CSP, Final Version 3.0 dated 08 March 2021, Table 7-1, p. 30.

4 TRIAL OBJECTIVES

4.1.1 Primary objective

To evaluate the efficacy of a Esflurbiprofen 165 mg Hydrogel Patch applied once a day compared with placebo in patients with acute blunt, soft tissue injuries of the limbs.

4.1.2 Secondary objectives

The secondary objectives are:

• To assess the efficacy of Esflurbiprofen Hydrogel Patch compared with placebo by means of secondary efficacy variables.

CRMB	Trial Substance:	Esflurbiprofen Hydrogel Patch	Study No.: EudraCT No.:	TK-254R-0201 2020-005165-14
	Short Title:	Local symptomatic and short-term treatment of pain in acute strains, sprains or bruises of the extremities following blunt trauma	Sponsor: TEIKO	KU SEIYAKU CO LTD.

• To assess the safety of Esflurbiprofen Hydrogel Patch compared with placebo applied once a day for up to seven days.

5 SUBJECTS ASSESSMENTS

5.1 Efficacy variables

5.1.1 Primary efficacy variable

The primary efficacy outcome is pain-on-movement (POM) change from baseline assessed by Visual Analogue Scale (VAS) to Visit 5 (72 hours after initiating treatment).

5.1.2 Secondary efficacy variables

- POM at injured site in mm measured using a 100 mm VAS at 12, 24, 48, 72, 96 and 168 hours after commencement of study treatment and will additionally presented by subgroups (table and Figure).
- AUC over time during first 12, 24, 48, 72, 96 and 168 hours for POM measured using a VAS; ordinate = POM score in mm, abscissa = time after treatment
- Pain-at-rest (PAR) at injured site in mm measured using a 100 mm VAS at 12, 24, 48 72, 96 and 168 hours.
- Reduction in VAS for POM from baseline:
 - Time to meaningful reduction (30%)
 - \circ Time to optimal reduction (50%)
 - Time to complete resolution of pain
- Responder rate 1 (defined as the proportion of patients achieving ≥50% reduction from baseline in the VAS score for POM at 72 hours)
- Responder rate 2 (defined as the proportion of patients able to resume training / normal physical activity by 168 hours)
- Clinical global assessment of efficacy as judged by investigator and patient at 48, 72 and 168 hours
- Overall dose of rescue medication needed (paracetamol).
- POM on VAS by indication at Visit 5.

Additional outcomes

- Adhesive power of patch (5-point scale)
- Mean adhesion by application site and/or net use.
- If there is significant use of rescue medication, a sensitivity analysis may be performed to assess impact on primary endpoint and responder rate.
- Outcomes will be compared for all use of rescue medication and separately for use to treat blunt trauma. Day 1 and the day of the final visit will count as full days for this purpose. Use of rescue medication on days after study medication has been discontinued will not be counted.
- POM on VAS difference at V4, V5, V6 compared to V1 (BL) (PID V4, PID V5, PID V6) PID V4, PID V5 and PID V6 will be compared between treatment groups using ANCOVA with terms in the model for treatment group, site [as fixed effects], and baseline POM assessment [as a covariate]. Least square mean for each treatment and the

CRMB	Trial Substance:	Esflurbiprofen Hydrogel Patch	Study No.: EudraCT No.:	TK-254R-0201 2020-005165-14
	Short Title:	Local symptomatic and short-term treatment of pain in acute strains, sprains or bruises of the extremities following blunt trauma		OKU SEIYAKU CO LTD.

corresponding difference between least square means with the p-value and 95 % confidence interval will be presented from the specified ANCOVA model.

• Sum of Pain Intensity differences (SPID) over 0-24, 0-48, 0-72 and 0-96 hours. SPID over 0-24, 0-48, 0-72 and 0-96 hours will be compared between treatment groups using ANCOVA with terms in the model for treatment group, site [as fixed effects], and baseline POM assessment [as a covariate]. Least square mean for each treatment and the corresponding difference between least square means (Active - placebo) with the p-value and 95 % confidence interval will be presented from the specified ANCOVA model.

5.2 Safety variables

The following parameters are recorded to assess the safety of the study drug:

- Adverse events (AEs). AEs will be documented at Visit 2 to Visit 7.
- Vital signs. Pulse rate (bpm) and blood pressure (BPs, BPd (mmHg) will be documented at the Baseline Visit (Visit 1) and Final Visit (Visit 7)).
- General physical examination.

Physical examination will be performed at Visit 1 (randomization visit) and at Visit 7 (final visit), as well as when judged necessary by the Investigator. Examination will include: general condition, dermatologic, eyes, ears, nose, throat, neck, thyroid, heart, respiratory system, abdomen, kidneys, skeletal system, extremities, lymphatic system, CNS, neurological conditions and other (to be specified).

• Height and weight.

Height in centimeters (cm, without shoes) and body weight (kg, in indoor clothing, but without shoes) will be measured at Visit 1. Body weight only will also be measured at Visit 7.

- Pregnancy and assessments of fertility. All women of child-bearing potential (WOCBP) and postmenopausal women who are not surgically sterile will have a urine pregnancy test with a dipstick at Visit 1 (Randomization Visit) at Visit 7 (Final Visit).
- Local tolerability

Local tolerability will be assessed by the Investigator according to the following numerical scale at Visits 3 to 7:

- 0: No evidence of irritation
- 1: Minimal erythema, barely perceptible
- 2: Definite erythema, readily visible; minimal edema or papular response
- 3: Erythema and papules
- 4: Definite edema
- 5: Erythema, edema, and papules
- 6: Vesicular eruption
- 7: Strong reaction spreading beyond test site

CRMB	Trial Substance:	Esflurbiprofen Hydrogel Patch	Study No.: TK-254R-0201 EudraCT No.: 2020-005165-14
	Short Title:	Local symptomatic and short-term treatment of pain in acute strains, sprains or bruises of the extremities following blunt trauma	Sponsor: TEIKOKU SEIYAKU CO LTD.

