Use of systemic or topical NSAIDs, analgesics (other than paracetamol), opioids, corticosteroids (except for topical treatment of bronchial asthma), heparin, or psychotropic agents, as well as the use of adhesive and fixing tapes and casts that would jeopardize the assessment of the primary variable (pain on movement).

3. Other treatments

. Ultrasound, physical therapy and acupuncture will not be allowed

Dosage Patients will be randomly assigned to one of the following treatment arms in a ratio of 1:1.

A: Esflurbiprofen Hydrogel Patch applied once per day to the affected injury site

B: Placebo patch applied once per day to the affected injury site

The dose regimen is a single hydrogel patch (investigational drug) applied topically to the injured site once a day for 7 days. The hydrogel patch should be positioned directly over the injury site and marked with a water-resistant pen to ensure the patch is applied at the same site throughout the study. The placebo patch (placebo) is identical in composition to the Esflurbiprofen 165 mg Hydrogel Patch, without the active ingredient. Placebo is applied as described for the investigational drug. Both patients and investigators will be blinded to study treatment. If the hydrogel patch begins to peel-off (>10% of the total surface), the edges of the topical system may be pressed down. If problems with adhesion persist, patients may overlay the topical systems applied to ankles, knees, or elbows). The mesh netting sleeve must allow air to pass through and not be occlusive (non-breathable)

Teikoku Chemical Co. Clinical Study Protocol	Ltd : TK-254R-0201	Confidential Final Version 3.0	Page 14
No. of Visits	A total of 7 visits		
Visit Schedule	 Visit 1 of Visit 2 of Visit 3 of Visit 4 of Visit 5 of Visit 6 of Visit 7 of 	n Day 1 (enrollment) n Day 1/2, depending on am/ n Day 2 (24 hours) n Day 3 (48 hours) n Day 4 (72 hours) n Day 5 (96 hours) n Day 8 (168 hours).	pm enrollment (12 hours)
Assessments	Efficacy will be a	assessed based on the followi	ng:
	 Primary assessme Pain-on-move standardized = 12, 24, 48, 72 Secondary assess AUC over time 	ent: cment (POM) measured by 10 movements as described in S d, 96 and 168 hours ments: me between baseline and the	00 mm VAS [performing ection 7.5.1] at baseline, first 12, 24, 48, 72, 96 and

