- Pain-at-rest (PAR) at injured site in mm measured using a 100 mm VAS at 12, 24, 48, 72, 96 and 168 hours
- □ Reduction in VAS for POM from baseline: o Time to meaningful reduction (30%)
 - o Time to optimal reduction (50%)
 - o Time to complete resolution of pain
- □ Responder rate 1 (defined as the proportion of patients achieving ≥50% reduction from baseline in the VAS score for POM at 72 hours)
- □ Responder rate 2 (defined as the proportion of patients able to resume training / normal physical activity by 168 hours)
- □ Clinical global assessment of efficacy as judged by investigator and patient at 48, 72 and 168 hours
- □ Overall dose of rescue medication needed (paracetamol)

Other:

- □ Adhesive power of patch (5-point scale)
- □ If there is significant use of rescue medication, a sensitivity analysis may be performed to assess impact on primary endpoint and responder rate.

Teikoku Chemical Co. Ltd Clinical Study Protocol : TK-254R-0201

Variables of
Tolerability andAdverse events, vital signs, physical examinations including local
examination for assessment of tolerability, sensitization & damage to
skin associated with patch removal (8-point scale).

Confidential

Final Version 3.0

1 Background

Blunt injuries consists of contusions, strains, sprains and combinations of thereof. Contusions are among the most common sports-related injuries [Best 1997, Nozaki 2008], second only to strains. Documented muscle contusions account for one third of all sports injuries. Most blunt injuries are unreported and untreated. They are caused by blunt trauma to skin, muscles, tendons and connective tissue structures resulting in tissue and cellular damage [Best 1997].

A blunt injury is aggravated by blood that has escaped from damaged capillaries into the interstitial tissues. Within a few hours after the injury, the presence of necrotic tissue and hematoma initiates an inflammatory reaction [Farges 2002]. Because inflammation initiates macrophage action with subsequent phagocytosis of necrotic debris and stimulation of capillary production, it is vital to the process of tissue regeneration. However, inflammation invariably causes edema that leads to anoxia and further cell death.

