Teikoku Chemical Co. Ltd Clinical Study Protocol : TK-254R-0201

Documentation of use of rescue medication, if needed (diary check).

- \square Record changes in the use of concomitant medication (section 6.5.6).
- \square Record information on AEs (section 8.1).
- \Box Spontaneous pain intensity, pain at rest (PAR) (section 7.5.1)
- \Box Injury site pain-on-movement (POM) (section 7.5.1).
- □ Visit 4: Global efficacy assessments (GEA) by patient and investigator (section 7.5.1).
- \Box Adhesive power of patch (section 7.5.1).
- □ Local tolerability assessment (except V2).

Visit 5 (72h \pm 4 h)

- \Box Apply next dose of study medication.
- □ Count used/unused patches & collect used patches.
- □ Check for last intake of rescue medication no later than 6 hours prior to Visit.
- □ Documentation of use of rescue medication
- \square Record changes in the use of concomitant medication (section 6.5.6).
- \square Record information on AEs (section 8.1).
- □ Spontaneous pain intensity, pain at rest (PAR) (section 7.5.1)
- \Box Injury site pain-on-movement (POM) (section 7.5.1).
- \Box Global efficacy assessments (GEA) by patient and investigator (section 7.5.1).
- Responder rate 1 (number of patients achieving 50% reduction from baseline in the VAS score for POM)
- \Box Adhesive power of patch (section 7.5.1).
- □ Local tolerability assessment.

Visit 6 (96h+4h)

- □ Apply next dose of study medication.
- □ Count used/unused patches and collect used patches.
- \Box Use of rescue medication.
- \square Record changes in the use of concomitant medication (section 6.5.6).
- \square Record information on AEs (section 8.1).
- \Box Spontaneous pain intensity, pain at rest (PAR) (section 7.5.1).
- \Box Injury site pain-on-movement (POM) (section 7.5.1).

- \Box Adhesive power of patch (section 7.5.1).
- □ Local tolerability assessment.
- □ Dispense patient card (section 6.5.7) and diary (section 6.5.8) and instruct patient about appropriate use.
- Dispense three patches to the patient.
- \Box The patient is instructed on the method and time of application of study drug (section 6.5.4).

Visit 7 (Day 8 ± 2 days) - Final visit

Procedures for this visit are also to be completed if the patient terminates the study prematurely.

- \Box Count used/unused patches and collect used patches.
- \square Record changes in the use of concomitant medication (section 6.5.6).
- \Box Record information on AEs (section 8.1).

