- 4 =very poor.
- □ "How do you rate this medication as a treatment for your soft tissue injury/contusion?" It is assessed on the following 5-point Likert scale:

0=excellent

1=very good

2=good

3=fair

4=poor

The global efficacy assessments are evaluated by the Investigator at Visits 4, 5 and 7 as the response to following questions:

• "Considering all the ways this treatment has affected the patient since he/she started in the study, how well is he/she doing?" It is assessed on the following 5-point Likert scale:

0 = very good

1 = good

2 = fair

3 = poor

4 = very poor.

Adhesive power of the patch

The adhesive power of the patch will be measured by a 5 point numerical scale ($0=\geq 90\%$ adhered / $1=\geq 75\%$ to <90% adhered / $2=\geq 50\%$ to <75% adhered / 3=>0% to <50% adhered / 4=completely detached) at every visit except V1.

Assessment of local tolerability of the patch

Local tolerability will be assessed by the Investigator according to the following numerical scale:

Score	Definition	
0	No evidence of irritation	
1	Minimal erythema, barely perceptible	
2	Definite erythema, readily visible, minimal edema or minimal papular response	
3	Erythema and papules	
4	Definite edema	
5	Erythema, edema and papules	
6	Vesicular eruption	
7	Strong reaction spreading beyond test site	

Use of rescue medication

Each use of rescue medication will be recorded in the CRF or in the diary. The Investigator/ the patient will record the date and time, the number of tablets taken and the reason for rescue (blunt trauma pain or other).

Resolution of soft tissue injury/contusion

Resolution of soft tissue injury/contusion is assessed by the Investigator at the final study visit. Time to resolution is the time of last application of study medication because the soft tissue injury/contusion has resolved. This is based on the record of applications of study medication and the assessments of efficacy.

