8.1 Adverse events

An adverse event (AE) is the appearance or worsening of any undesirable sign, symptom, or medical condition occurring after starting the study drug even if the event is not considered to be related to study drug. Study drug includes the investigational drug under evaluation and the comparator drug or placebo that is given during any phase of the study. Medical conditions/diseases present before starting study drug are only considered adverse events if they worsen after starting study drug

The occurrence of adverse events should be sought by non-directive questioning of the patient at each visit during the study. Adverse events also may be detected when they are volunteered

by the patient during or between visits or through physical examination, , or other assessments. All adverse events must be recorded on the Adverse Events CRF with the following information:

- 1. the severity grade (mild, moderate, severe)
- 2. its relationship to the study drug(s) (suspected/not suspected)
- 3. its duration (start and end dates or if continuing at final exam)
- 4. whether it constitutes a serious adverse event (SAE)

An SAE is defined as an event which:

- \Box is fatal or life-threatening
- □ results in persistent or significant disability/incapacity
- □ constitutes a congenital anomaly/birth defect
- □ requires inpatient hospitalization or prolongation of existing hospitalization, unless hospitalization is for:
 - o elective or pre-planned treatment for a pre-existing condition that is unrelated to the indication under study and has not worsened since the start of study drug
 - o treatment on an emergency outpatient basis for an event not fulfilling any of the definitions of a SAE given above and not resulting in hospital admission
 - o social reasons or respite care in the absence of any deterioration in the patient's general condition
- □ is medically significant, i.e., defined as an event that jeopardizes the patient or may require medical or surgical intervention to prevent one of the outcomes listed above.

Unlike routine safety assessments, SAEs are monitored continuously and have special reporting requirements.

All AEs and SAEs will be recorded, including their severity, their duration and relationship to study drug.

All adverse events should be treated appropriately. Treatment may include one or more of the following:

- \Box no action taken (i.e., further observation only);
- □ study drug dosage temporarily interrupted;

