14.5.2 Other Variables Related to Safety

Summary statistics for the absolute vital sign value and the changes from baseline will be presented using n, mean, standard deviation, median, minimum, and maximum.

Abnormal observations on physical examinations will be listed.

Furthermore, weight, pregnancy and assessments of fertility data will only be listed.

Local tolerability assessment will be summarized descriptively by visit.

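### Local tolerability has no pre-patch score at Visit 1 and is summarized only by visit, so erythema or edema of the fresh injury may be mixed with patch reactions

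*SAP*

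**What the plan says.** **Timing.** SAP 5.2 states: "Local tolerability will be assessed by the Investigator according to the following numerical scale at Visits 3 to 7". The protocol synopsis (safety assessments), the visit lists in Protocol Section 7, Protocol Table 7-1 and the schedule in SAP 5.5.1 agree: no score at Visit 1 or Visit 2. At Visit 1 the protocol asks for the size and location of the injury, an examination of it, and a brief general physical examination with a dermatologic item. None of these uses the tolerability scale.

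**Scale.** Protocol 7.5.1 introduces it with "Local tolerability will be assessed by the Investigator according to the following numerical scale". It runs from 0 to 7. Grade 1 is faint erythema. Grade 2 reads in the SAP "2: Definite erythema, readily visible; minimal edema or papular response". Grade 3 is erythema with papules, grade 4 is edema alone, grade 5 combines erythema, edema and papules, grade 6 is vesicular, and grade 7 is a strong reaction that extends past the application site. Neither document has a rule for signs that belong to the injury.

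**Placement.** The synopsis says under dosage: "The hydrogel patch should be positioned directly over the injury site". Patients enter within 6 hours of an injury of 25 to 120 cm² (Protocol 5.1). The background section says: "However, inflammation invariably causes edema that leads to anoxia and further cell death". Protocol Section 2 expects that early treatment may lessen swelling.

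**Analysis.** SAP 14.5.2: "Local tolerability assessment will be summarized descriptively by visit". SAP 5.4 foresees changes from Visit 1 for quantitative variables, but this score has no Visit 1 value. Acceptable local tolerability is part of the synopsis objective.

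**The concern.** The scale grades the same kinds of sign that a fresh blunt injury can produce, at the same place, and nothing on the scale records what was there before the patch. A score of 1, 2 or 4 at Visit 3 could be a patch reaction, the injury, or both.

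Three things are at stake. Absolute rates of local reaction may be too high in both arms. A real difference between arms may be diluted by a shared background of injury signs. And because the active patch is expected to reduce swelling, that background may fall faster on active, which would make active look better tolerated than it is.

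Separately, tables by visit do not show how many patients ever reached a given score.

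**Working it through.** The documents give no figure for local tolerability, so there is none to reproduce. The sample size concerns the primary endpoint and is not affected. The documents also give no rate of injury erythema or edema, so every rate below is an assumption chosen to show direction and range.

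**1. Which grades can overlap with the injury.** Grades 1, 2 and 4 can be met by erythema or edema alone. Grades 3 and 5 need papules and grade 6 needs vesicles; nothing in the documents ties these to blunt injury. Grade 7 is defined by spread. The overlap is therefore real but partial.

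**2. Model.** Let *b* be the share of placebo patients with injury signs that would score at the visit, *r* the relative reduction of those signs on active, and *i* the true irritation rate, independent of injury signs. Then

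- placebo observed = 1 − (1 − b)(1 − i_P)
- active observed = 1 − (1 − b(1 − r))(1 − i_A)

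**3. First set: i_A = 5%, i_P = 1% (true difference +4 points), r = 25%.**

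| b | Active | Placebo | Difference (points) |
|---|---|---|---|
| 20% | 1 − 0.85 × 0.95 = 19.25% | 1 − 0.80 × 0.99 = 20.8% | −1.55 |
| 40% | 1 − 0.70 × 0.95 = 33.5% | 1 − 0.60 × 0.99 = 40.6% | −7.1 |
| 60% | 1 − 0.55 × 0.95 = 47.75% | 1 − 0.40 × 0.99 = 60.4% | −12.65 |

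With r = 0 and b = 40%, active is 1 − 0.60 × 0.95 = 43.0% and the difference is +2.4. The direction is then right, but the observed rates are 41% to 43% against true rates of 1% and 5%.

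**4. Second set: i_A = 15%, i_P = 5% (true difference +10 points), 100 patients per arm.**

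| b | Placebo | Active, r = 0 | Difference (points) | 95% CI half-width (points) | Placebo scorers with injury signs only | r at which the difference is zero |
|---|---|---|---|---|---|---|
| 0 | 5% | 15% | 10 | 8.2 | – | – |
| 20% | 24% | 32% | 8 | 12.4 | 0.19/0.24 = 79% | 47% |
| 40% | 43% | 49% | 6 | 13.8 | 0.38/0.43 = 88% | 18% |
| 60% | 62% | 66% | 4 | 13.3 | 0.57/0.62 = 92% | 8% |

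Half-width = 1.96 × √[p(1 − p)/100 + a(1 − a)/100], with p and a the observed placebo and active rates. The zero point solves (1 − b(1 − r)) × 0.85 = (1 − b) × 0.95. The background both shrinks the contrast and widens its interval.

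**5. What a Visit 1 score would recover.** Take the 40% case of step 3 and suppose that half of the signs arise after Visit 1. New signs are then 20% on placebo and 15% on active. Increase over Visit 1: active 1 − 0.85 × 0.95 = 19.25%, placebo 1 − 0.80 × 0.99 = 20.8%, difference −1.55 points. If irritation cannot raise a score that was already positive at Visit 1 (20% per arm), active is 0.15 + 0.05 × 0.65 = 18.25%, placebo is 0.20 + 0.01 × 0.60 = 20.6%, and the difference is −2.35. Either result is closer to +4 than −7.1 is, but the sign is still wrong.

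**6. Order of the grades.** Edema alone is 4, and erythema with papules is 3. A patient at 4 on Visit 1 whose edema clears and who then develops papules moves from 4 to 3 and shows no increase. Change scores therefore need the separate count of grades 3, 5, 6 and 7.

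**The case against.** The case on the other side has force, and much of it stands.

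- **The construct is stated.** The synopsis describes the measure as a skin reaction or damage noticed when the patch is taken off, and score 0 is worded as absence of irritation. A reader might infer that sites following the scale must record injury swelling as a patch reaction. The documents do not say so; an investigator may discount injury signs. But that would rest on unstated personal judgment at three sites.
- **Placebo control.** Injury signs are balanced on average at entry. This protects the direction of the comparison when the drug leaves those signs unchanged (+2.4, step 3). It does not protect absolute rates or prevent dilution, and it does not cover a drug effect on swelling.
- **Adverse events.** Safety rests mainly on adverse events, which may be found through examination and are tabulated as numbers of patients (SAP 14.5.1). A reader might infer that patients reacting at different visits are never counted together. That is true of the score table only.
- **The worsening rule.** Protocol 8.1 says: "Medical conditions/diseases present before starting study drug are only considered adverse events if they worsen after starting study drug". A reader might infer that this cannot be applied to local signs. It can, by clinical comparison with the Visit 1 examination; what is missing is a reference on the scale.
- **Exclusions.** Open wounds and current skin disorders at the site are excluded. Injury erythema and edema are not.
- **Limits of the remedy.** Inflammation starts within a few hours, so swelling can appear after Visit 1 and count as an increase. This stands (step 5).

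**Conclusion.** The gap is real. There is no pre-patch value on the tolerability scale, and the score is summarized only by visit, although three of its grades can overlap with signs of the injury under the patch. Raw scores may therefore overstate absolute reaction rates, dilute the contrast between arms and, if the active patch reduces swelling, favour active.

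The size is unknown. The figures above rest on assumed irritation rates, assumed injury signs in 20% to 60% of patients, and independence of the two. The negative differences also need an assumed reduction of injury signs on active. It would be tempting to conclude that the trial will hide drug irritation, or that by-visit tables understate the number of patients who react fivefold. The documents support neither. The first depends on rates they do not give, and the second is a ceiling reached only if different patients react at each of the five scored visits.

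The synopsis wording, the Visit 1 examination, the placebo arm and the patient-level adverse event tables limit the problem, but none supplies a baseline on the scale. In a proof-of-concept trial with descriptive safety and no tolerability threshold, this is minor to moderate, with moderate confidence in the consequences.

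**What to change.** 1. Score the intended application site on the same 8-point scale at Visit 1, before the first patch. Amend Protocol Section 7, Table 7-1, SAP 5.2 and SAP 5.5.1. This is the only score on the scale that cannot be due to the patch.
2. In SAP 14.5.2, add by arm each patient's worst post-baseline score and worst increase over Visit 1. Keep the by-visit table.
3. Tabulate grades 3, 5, 6 and 7 (papules, vesicles or spread beyond the site) separately. Grade 2 also admits a slight papular response, so this count is not exhaustive.
4. State in the SAP that change from Visit 1 reduces the confounding but does not remove it, because injury swelling can appear later and the grades are not strictly ordered.

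If Visit 1 scoring can no longer be added, the table of worst scores and the separate count in item 3 can still enter the SAP before unblinding, since SAP Section 1 has it finalized after the blind review meeting.

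**Cost.** A small amendment to the schedule and CRF (one field, at a visit where the injury is already examined) and a little more tabulation. Sample size, alpha and treatment are unchanged.
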